10.6.2.4 Handling of Missing Data for Statistical Analysis

Element	Reporting Detail
Imputation	
 No imputation will be performed for missing data

10.7 Appendix 7: Values of Potential Clinical Importance

10.7.1 Laboratory Values

Haematology				
Laboratory Parameter	Units	Category	Clinical Concern Range	
			Low Flag (< x)	High Flag (>x)
Hematocrit	Ratio of 1	Male		0.54
		Female		0.54
		Δ from BL	↓0.075	
Hemoglobin	g/L	Male		180
		Female		180
		Δ from BL	↓25	
Lymphocytes	x10 ⁹ / L		0.8	
Neutrophil Count	x10 ⁹ / L		1.5	
Platelet Count	x10 ⁹ / L		100	550
White Blood Cell Count (WBC)	x10 ⁹ / L		3	20

Clinical Chemistry				
Laboratory Parameter	Units	Category	Clinical Concern Range	
			Low Flag (< x)	High Flag (>x)
Albumin	mmol/L		30	
Calcium	mmol/L		2	2.75
Creatinine	mmol/L	Δ from BL		↑ 44.2
Glucose	mmol/L		3	9
Potassium	mmol/L		3	5.5
Sodium	mmol/L		130	150

Liver Function				
Test Analyte	Units	Category	Clinical Concern Range	
ALT/SGPT	U/L	High	≥ 2x ULN	
AST/SGOT	U/L	High	≥ 2x ULN	
AlkPhos	U/L	High	≥ 2x ULN	
T Bilirubin	µmol/L	High	≥ 1.5xULN	
T. Bilirubin + ALT	µmol/L U/L	High	1.5xULN T. Bilirubin + ≥ 2x ULN ALT	

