5.4.3. Haematology Stopping Criteria

Study treatment will be discontinued for a subject if the following haematology stopping criteria are met and subjects should be followed up until values are not clinically significant.

- A reduction in haemoglobin to below 110 g/L in males and below 100 g/L in females
- A reduction in neutrophil count to below 1000/mm³ (1.0x10⁹/L)
- A reduction in lymphocyte count to below 500/mm³ (0.5x10⁹/L)

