5.4.4. Vital Signs Stopping Criteria

Study treatment will be discontinued for a subject if the following vital signs stopping criteria are met:

- Clinically significant and sustained increase in resting heart rate (for example, >120 beats/minute for more than 2 hours)
- Clinically significant and sustained change in blood pressure (for example, systolic blood pressure >150 mm Hg or <85 mm Hg for more than 2 hours, or diastolic blood pressure >95 mm Hg for more than 2 hours)

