10.7.3 Vital Signs

Vital Sign Parameter (Absolute)	Units	Clinical Concern Range	
		Lower	Upper
Systolic Blood Pressure	mmHg	< 85	> 160
Diastolic Blood Pressure	mmHg	< 45	> 100
Heart Rate	bpm	< 40	> 110

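### SAP Appendix 7: the creatinine and albumin limits carry unusable units, the upper blood-pressure and haemoglobin flags miss values at the protocol's stopping limits, and the laboratory limits feed no display

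*SAP*

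**What the plan says.** SAP Appendix 7 holds the PCI limits. In 10.7.1 the creatinine row is "Creatinine mmol/L Δ from BL ↑ 44.2" and the albumin row is "Albumin mmol/L 30", the latter in the low-flag column. The bilirubin row of the same section uses a different unit: "T Bilirubin µmol/L High". For haemoglobin the absolute entries are high flags only ("Hemoglobin g/L Male 180", with the same number for women). The low side has only a change from baseline, "Δ from BL ↓25".

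In 10.7.3 the systolic row is "Systolic Blood Pressure mmHg < 85 > 160". Diastolic pressure is flagged below 45 or above 100 mmHg.

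Protocol 5.4.3 discontinues study treatment on "A reduction in haemoglobin to below 110 g/L in males and below 100 g/L in females". Protocol 5.4.4 does so for a blood-pressure change that is both clinically significant and sustained. It gives as examples "systolic blood pressure >150 mm Hg or <85 mm Hg for more than 2 hours, or diastolic blood pressure >95 mm Hg", the diastolic value also for more than 2 hours.

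On outputs, SAP 8.3 (Table 8) and 10.10.10 plan PCI listings for ECG (Listing 28) and vital signs (Listing 32). SAP 8.2 (Table 7), 10.10.7 and 10.10.10 plan none for laboratory values.

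**The concern.** A PCI limit exists to pick out the readings that deserve a second look. It should be expressed in a unit in which it can discriminate. It should also not be looser than a value at which the same trial would stop a subject's treatment. Two rows fail the first test, and the upper blood-pressure and low haemoglobin limits fail the second.

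Protocol 4.6.1 names both haemodynamic change and a fall in red cell count or haemoglobin as risks of this compound, so these are not incidental parameters. At stake is the usefulness of Listing 32, and whether the laboratory limits mean anything if they are programmed as printed.

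**Working it through.** **Step 1: units.** The documents give no molar masses. I assume 113.1 g/mol for creatinine and 65-69 kg/mol for albumin.

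- Creatinine as printed: 44.2 mmol/L × 113.1 g/mol = 5.0 g/L, about 500 mg/dL.
- Creatinine in µmol/L: 44.2 µmol/L × 113.1 g/mol = 5.0 mg/L = 0.50 mg/dL. This is a round figure and exactly 1,000 times smaller, which points to a unit slip.
- Albumin as printed: 30 mmol/L × 65-69 kg/mol = 1,950-2,070 g/L, more than a litre of plasma weighs.
- Albumin in g/L: 30 g/L is 0.43-0.46 mmol/L. An assumed normal value of 45 g/L is 0.65-0.69 mmol/L, so a flag below 30 mmol/L catches every sample.

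The micromolar symbol is intact in the bilirubin row of the same section, so the printed unit is unlikely to be a text-conversion fault.

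**Step 2: every SAP limit that has a matching protocol criterion.** The protocol values come from 5.4.2 to 5.4.4 and Appendix 4.

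| Parameter | SAP flag | Protocol value | Unflagged values |
|---|---|---|---|
| Systolic, high (mmHg) | >160 | >150 (example, sustained) | 151-160 |
| Diastolic, high (mmHg) | >100 | >95 (example, sustained) | 96-100 |
| Systolic, low (mmHg) | <85 | <85 (example, sustained) | none |
| Heart rate (beats/min) | >110 | >120 (example, sustained) | none |
| Haemoglobin, low (g/L) | fall of 25 | <110 men, <100 women | see step 3 |
| Neutrophils (×10⁹/L) | <1.5 | <1.0 | none |
| Lymphocytes (×10⁹/L) | <0.8 | <0.5 | none |
| ALT (× ULN) | ≥2 | ≥3 | none |
| QTc, absolute (msec) | >450 | >500 | none |
| QTc, increase (msec) | >60 | >60 | none |

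**Step 3: haemoglobin.** Let b be the baseline, v the later value and L the protocol limit, all in whole g/L. A value meets the protocol criterion but is not flagged when v < L and b − v ≤ 25. The largest such v is L − 1, so b can be as high as (L − 1) + 25 = L + 24.

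- Men: 110 + 24 = 134.
- Women: 100 + 24 = 124.
- If a fall of exactly 25 counts as flagged, which the table does not settle, the bounds are 133 and 123.
- Example: a man going from 130 to 108 g/L has a fall of 22. He is below 110 and not flagged.

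Falls of this size match what protocol 4.6.1 reports in animals: 10-13% in rats and about 10% in dogs, against controls. This is an illustration, not a prediction for humans. A 13% fall takes a man from 126 to 126 × 0.87 = 109.6 g/L (fall 16.4) and a woman from 114 to 114 × 0.87 = 99.2 g/L (fall 14.8). Both are below the protocol limit and well short of a 25 g/L fall. Protocol 5.1 and 5.2 state no numerical haemoglobin minimum that would exclude such baselines.

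**Step 4: where the limits are used.** The ECG limits feed Listing 28 and the vital-sign limits feed Listing 32. The laboratory limits feed nothing. The general counting rule in SAP 10.5.1 mentions PCI summary tables, but Appendix 10 contains no such table for any type of data.

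**The case against.** The strongest reply is that little follows from these discrepancies, and much of it stands.

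- **Nothing is lost from reporting.** Chemistry, haematology and vital signs have full listings (20-23, 30-31) and summaries (Tables 3.13-3.20, 3.29-3.32). Withdrawals and treatment discontinuations have Listings 2 and 3, and adverse events leading to withdrawal have Listing 18. With at most 18 + 40 = 58 planned subjects, a sustained 155/98 mmHg or a haemoglobin of 108 g/L would be visible in those listings.
- **No laboratory PCI display exists.** The unit errors and the haemoglobin gap therefore distort no current output. Only Listing 32 is affected as planned.
- **The blood-pressure comparison is not like for like.** The protocol's values are examples that also need clinical significance and more than 2 hours' duration, whereas a PCI flag applies to one reading. Neither document requires the PCI range to contain the stopping examples. Blood pressure fell in dogs, the species with the valvular and vascular lesions. It rose in rats, however, so the high side is not irrelevant.

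A reader might infer that Appendix 7 fails as a whole, but step 2 shows that the other matched limits flag at or before the stopping value. A reader might also infer that the PCI limits define the primary safety endpoint. Neither document says so: protocol 7.2.7 and Appendix 2 leave clinical relevance to the investigator. Nor is subject protection weakened, because the stopping criteria operate without reference to these flags.

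The reply does not rescue the entries themselves. A limit that can never trigger, and one that always does, are wrong as written. A listing meant to highlight notable blood pressures should not leave out readings that can contribute to a protocol stop.

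**Conclusion.** The point holds as a reporting defect confined to the named entries. Creatinine carries a unit 1,000 times too large, and albumin a unit in which every sample is flagged. Systolic readings of 151-160 mmHg and diastolic readings of 96-100 mmHg would be missing from Listing 32, although they can contribute to a stop under protocol 5.4.4. Men with baselines up to 134 g/L and women up to 124 g/L (133 and 123 on the other reading of the 25 g/L limit) can cross the haemoglobin criterion unflagged. The laboratory limits are printed but unused.

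The unit conclusion rests on assumed molar masses but does not depend on their exact values. The blood-pressure and haemoglobin conclusions come directly from the two documents. No estimate, dose-escalation rule or stopping rule is affected.

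**What to change.** 1. In SAP 10.7.1, change the creatinine unit to µmol/L and the albumin unit to g/L, after confirming the units that the local laboratory reports.
2. Reconcile the reporting flags in SAP 10.7.1 and 10.7.3 with the existing limits in protocol 5.4.3 and 5.4.4, so that any value meeting a protocol limit is also flagged. State whether a haemoglobin fall of exactly 25 g/L counts.
3. Add a by-part listing of laboratory PCI values to SAP Appendix 10, alongside Listings 28 and 32, so that the laboratory limits are used.

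The protocol's stopping criteria are not changed. The cost is a few table edits and one listing from data already collected. The downside is a few more flagged rows.

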10.7.2 ECG

ECG Parameter	Units	Clinical Concern Range	
		Lower	Upper
Absolute			
Absolute QTc Interval	msec		> 450
Absolute PR Interval	msec	< 110	> 220
Absolute QRS Interval	msec	< 75	> 110
Change from Baseline			
Increase from Baseline QTc	msec		> 60

10.7.3 Vital Signs

Vital Sign Parameter (Absolute)	Units	Clinical Concern Range	
		Lower	Upper
Systolic Blood Pressure	mmHg	< 85	> 160
Diastolic Blood Pressure	mmHg	< 45	> 100
Heart Rate	bpm	< 40	> 110

10.8 Appendix 8: Model Checking and Diagnostics for Statistical Analyses

10.8.1 Statistical Analysis Assumptions

Endpoint(s)	
• PK End points AUC and Cmax
Analysis	
• Mixed Model

Assumptions:

- For the Mixed Model, model assumptions will be checked, and appropriate adjustments may be applied based on the data.
- Distributional assumptions underlying the model used for analysis will be examined by obtaining a normal probability plot of the residuals and a plot of the residuals versus the fitted values (i.e. checking the normality assumption and constant variance assumption of the model respectively) to gain confidence that the model assumptions are reasonable.
- If there are any departures from the distributional assumptions, alternative transformations, such as data squared or square root of data, will be explored.
- Non-parametric analyses will be conducted if the normality assumption does not hold.

10.9 Appendix 9 : Abbreviations & Trade Marks

10.9.1 Abbreviations

μg	Microgram
λ_z	Terminal phase rate constant
AE	Adverse Event
Ae	Excretion of unchanged drug
AIC	Akaike's Information Criteria
ALT	Alanine aminotransferase (SGPT)
ANOVA	Analysis of Variance
AST	Aspartate aminotransferase (SGOT)
AUC	Area under concentration-time curve
AUC(0- ∞)	Area under the concentration-time curve from time zero (pre-dose) extrapolated to infinite time
AUC(0-t)	Area under the concentration-time curve from time zero (pre-dose) to last time of quantifiable concentration within a subject across all treatments
AUC(0- τ)	Area under the concentration-time curve from time zero (pre-dose) during a dosage interval
AUC(Ro)	Observed Accumulation Ratio for AUC observed accumulation ratio for AUC
AUC[0-24]	Area under the concentration-time curve from time zero (pre-dose) to 24 hours post dose
BMI	Body mass index
BUN	Blood urea nitrogen
CDISC	Clinical Data Interchange Standards Consortium
CI	Confidence Interval
CL	Clearance
CL _r	Renal Clearance
C_{max}	Maximum observed concentration
CPMS	Clinical Pharmacology Modelling and Simulation
CPSR	Clinical Pharmacology Study Report
CPSSO	Clinical Pharmacology Sciences and Study Operations
CRF	Case Report Form
C _T	Trough concentration (C _T)
CV	Coefficient of variance
DBR	Database Release
DEC	Dose Escalation Committee
DP's	Decimal places
ECG	Electrocardiogram
ESS	Effective sample size
fe	Fraction of the dose excreted in urine
GSK	GlaxoSmithKline
h	Hour
HARP	Harmonized Analysis and Reporting Process
Hg	Mercury

ICH	International Conference on Harmonisation
IDSL	Integrated Data Standards Library
kg	Kilogram
L	Litres
MCMC	Markov Chain Monte Carlo
MCSE	Monte Carlo Standard Error
mg	Milligram
mL	Millilitre
mm	Millimetre
MM	Mixed Model
nm	Nanometer
NOAEL	No Observed Adverse Effect Level
PK	Pharmacokinetic
PTS	Platform Technologies and Science
QSI	Quantitative Sciences India
QTc	Electrocardiogram QT interval corrected for heart rate
QTcF	Electrocardiogram QT interval corrected for heart rate using Fridericia's formula
RCmax	Cmax Ratio
RAP	Reporting and Analysis Plan
RBC	Red blood cells
Rss	Steady-State Ratio
SAC	Statistical Analysis Complete
SAE	Serious adverse event(s)
SAS	Statistical Analysis System
SD	Standard Deviation
SGOT	Serum glutamic-oxaloacetic transaminase
SGPT	Serum glutamic pyruvic transaminase
SPDS	Statistics, Programming and Data Sciences
t½	Terminal phase half-life
Tmax	Time of occurrence of Cmax
TB	Tuberculosis
tmax	Time of occurrence of Cmax
ULN	Upper Limit of Normal
WBC	White blood cells

10.9.2 Trademarks

Trademarks of the GlaxoSmithKline group of companies	Trademarks not owned by the GlaxoSmithKline group of companies
NONE	R SAS WinNonlin

10.10 Appendix 10: List of Data Displays

10.10.1 Data Display Numbering

The following numbering will be applied for RAP generated displays:

Section	Tables	Figures
Study Population	1.1 to 1.23	N/A
Pharmacokinetic	2.1 to 2.15	2.1 to 2.8
Safety	3.1 to 3.32	N/A
Dose Escalation	4.1 to 4.2	4.1 to 4.4
Section	Listings	
ICH Listings	1 to 32	
Other Listings	33 to 41	

10.10.2 Mock Example Shell Referencing

Non IDSL specifications will be referenced as indicated and if required an example mock-up displays provided in [Appendix 11: Example Mock Shells for Data Displays](#).

Section	Figure	Table	Listing
Pharmacokinetic		PK_Tn	
Dose Escalation	DE_Fn	DE_Tn	

NOTES:

- Non-Standard displays are indicated in the 'IDSL / TST ID / Example Shell' or 'Programming Notes' column as '[Non-Standard] + Reference.'

10.10.3 Deliverable

Delivery	Description
DE	Dose Escalation
SAC	Statistical Analysis Complete

10.10.4 Study Population Tables

Study Population Tables					
No.	Population	IDSL / TST ID / Example Shell	Title	Programming Notes	Deliverable [Priority]
Subject Disposition					
1.1.	Enrolled	ES4	Summary of Subject Disposition – Part A		SAC
1.2.	Enrolled	ES4	Summary of Subject Disposition – Part B		SAC
1.3.	Enrolled	ES6	Summary of Screening Status and Reasons for Screen Failure – Part A		SAC
1.4.	Enrolled	ES6	Summary of Screening Status and Reasons for Screen Failure – Part B		SAC
1.5.	Safety	SD1	Summary of Reasons for Study Treatment Discontinuation – Part B		SAC
1.6.	Safety	ES1	Summary of Reasons for Study Withdrawal during the Study – Part A		SAC
1.7.	Safety	ES1	Summary of Reasons for Study Withdrawal during the Study – Part B		SAC
1.8.	Safety	IE1	Summary of Inclusion/Exclusion Criteria Deviations – Part A		SAC
1.9.	Safety	IE1	Summary of Inclusion/Exclusion Criteria Deviations – Part B		SAC

Study Population Tables					
No.	Population	IDSL / TST ID / Example Shell	Title	Programming Notes	Deliverable [Priority]
Protocol Deviation					
1.10.	Safety	DV1	Summary of Important Protocol Deviations – Part A		SAC
1.11.	Safety	DV1	Summary of Important Protocol Deviations – Part B		SAC
Population Analysed					
1.12.	Safety	SP1	Summary of Study Populations – Part A		SAC
1.13.	Safety	SP1	Summary of Study Populations – Part B		SAC
Demography					
1.14.	Safety	DM1	Summary of Demographic Characteristics – Part A	Include BMI	SAC
1.15.	Safety	DM1	Summary of Demographic Characteristics – Part B	Include BMI	SAC
1.16.	Safety	DM5	Summary of Race and Racial Combinations – Part A		SAC
1.17.	Safety	DM5	Summary of Race and Racial Combinations – Part B		SAC
Concomitant Medications					
1.18.	Safety	CM1	Summary of Concomitant Medications – Part A		SAC
1.19.	Safety	CM1	Summary of Concomitant Medications – Part B		SAC

Study Population Tables					
No.	Population	IDSL / TST ID / Example Shell	Title	Programming Notes	Deliverable [Priority]
Exposure and Treatment Compliance					
1.20.	Safety	EX1	Summary of Exposure to Study Drug – Part A		SAC
1.21.	Safety	EX1	Summary of Exposure to Study Drug – Part B		SAC
1.22.	Safety	COMPL1	Summary of Overall Compliance Based on Exposure – Part A		SAC
1.23.	Safety	COMPL1	Summary of Overall Compliance Based on Exposure – Part B		SAC

10.10.5 Pharmacokinetic Tables

Pharmacokinetic Tables					
No.	Population	IDSL / TST ID / Example Shell	Title	Programming Notes	Deliverable [Priority]
Pharmacokinetic					
2.1.	PK	PK01	Summary of Plasma GSK3036656 Pharmacokinetic Concentration-Time data – Part A		SAC
2.2.	PK	PK01	Summary of Plasma GSK3036656 Pharmacokinetic Concentration-Time data – Part B		SAC

Pharmacokinetic Tables					
No.	Population	IDS L / TST ID / Example Shell	Title	Programming Notes	Deliverable [Priority]
2.3.	PK	PK02	Summary of Pharmacokinetic Urine Excretion Rate-Time Data – Part A		SAC
2.4.	PK	PK02	Summary of Pharmacokinetic Urine Excretion Rate-Time Data – Part B		SAC
2.5.	PK	PK03	Summary of Derived Plasma GSK3036656 Pharmacokinetic Parameters (untransformed data) – Part A		SAC
2.6.	PK	PK03	Summary of Derived Plasma GSK3036656 Pharmacokinetic Parameters (untransformed data) – Part B		SAC
2.7.	PK	PK05	Summary of Derived Plasma GSK3036656 Pharmacokinetic Parameters (log-transformed data)– Part A		SAC
2.8.	PK	PK05	Summary of Derived Plasma GSK3036656 Pharmacokinetic Parameters (log-transformed data)– Part B		SAC
2.9.	PK	Non- Standard PK_T1	Statistical Analysis of log transformed plasma GSK3036656 Pharmacokinetic Parameters Assessing Dose Proportionality (Power Model) – Part A	AUC(0-t), AUC(0-∞) and Cmax	SAC
2.10.	PK	Non- Standard PK_T1	Statistical Analysis of log transformed plasma GSK3036656 Pharmacokinetic Parameters Assessing Dose Proportionality (Power Model) – Part B	AUC(0-τ) and Cmax	SAC
2.11.	PK	Non- Standard PK_T2	Statistical Analysis of log transformed plasma GSK3036656 Pharmacokinetic Parameters Assessing Food Effect– Part A	Only for Single Dose Study Phase: AUC(0-t), AUC(0-∞), Cmax and t _{1/2}	SAC

Pharmacokinetic Tables					
No.	Population	IDSL / TST ID / Example Shell	Title	Programming Notes	Deliverable [Priority]
2.12.	PK	Non-Standard PK_T3	Non-Parametric Analysis of Pharmacokinetic Parameter Assessing Food Effect -Tmax – Part A	Only for Single Dose Study Phase: T-max	SAC
2.13.	PK	Non-Standard PK_T4	Statistical Analysis of log transformed plasma GSK3036656 Pharmacokinetic Parameters Assessing Time Invariance– Part B	Only for Repeat Dose Study Phase	SAC
2.14.	PK	Non-Standard PK_T5	Statistical Analysis of log transformed plasma GSK3036656 Pharmacokinetic Parameters Assessing Accumulation Ratio– Part B	Only for Repeat Dose Study Phase; AUC(Ro) and RCmax	SAC
2.15.	PK	Non-Standard PK_T6	Statistical Analysis of log transformed plasma GSK3036656 Pharmacokinetic Parameters Assessing Steady State– Part B	Only for Repeat Dose Study Phase	SAC

10.10.6 Pharmacokinetic Figures

Pharmacokinetic Figures					
No.	Population	IDSL / TST ID / Example Shell	Title	Programming Notes	Deliverable [Priority]
Pharmacokinetic					
2.1.	PK	PK16a	Individual Subject Plasma GSK3036656 Concentration-time Plot (Linear and Semi-log) by Subject	By part	SAC

Pharmacokinetic Figures					
No.	Population	IDSL / TST ID / Example Shell	Title	Programming Notes	Deliverable [Priority]
2.2.	PK	PK24	Individual Subject Plasma GSK3036656 Concentration-time Plot (Linear and Semi-log) by Treatment	By part	SAC
2.3.	PK	PK17	Mean Plasma GSK3036656 Concentration-Time Plots (Linear and Semi-log) by treatment	By part	SAC
2.4.	PK	PK18	Median Plasma GSK3036656 Concentration-Time Plots (Linear and Semi-log) by treatment	By part	SAC
2.5.	PK	PK21	Individual Urine Excretion Rate-Time Plots (Linear and Semi-log) by subject	By part	SAC
2.6.	PK	PK22	Mean Urine Excretion Rate-Time Plots (Linear and Semi-log) by treatment	By part	SAC
2.7.	PK	PK23	Median Urine Excretion Rate-Time Plots (Linear and Semi-log) by treatment	By part	SAC
2.8.	PK	PK25	Comparative Plot of Individual Subject Plasma GSK3036656 Pharmacokinetic Parameter Versus Treatment	By part	SAC

10.10.7 Safety Tables

Safety Tables					
No.	Population	IDSL / TST ID / Example Shell	Title	Programming Notes	Deliverable [Priority]
Adverse Events					
3.1.	Safety	AE1	Summary of All Adverse Events by System Organ Class and Preferred Term – Part A		SAC
3.2.	Safety	AE1	Summary of All Adverse Events by System Organ Class and Preferred Term – Part B		SAC
3.3.	Safety	AE3	Summary of Serious Adverse Events – Part A		SAC
3.4.	Safety	AE3	Summary of Serious Adverse Events – Part B		SAC
3.5.	Safety	AE3	Summary of Drug Related Adverse Events – Part A		SAC
3.6.	Safety	AE3	Summary of Drug Related Adverse Events – Part B		SAC
3.7.	Safety	AE3	Summary of Adverse Events Leading Withdrawal from Study – Part A		SAC
3.8.	Safety	AE3	Summary of Adverse Events Leading Withdrawal from Study – Part B		SAC
3.9.	Safety	AE15	Summary of Common (>=5%) Non-serious Adverse Events by System Organ Class and Preferred Term (Number of Subjects and Occurrences) - Part A		SAC

Safety Tables					
No.	Population	IDSL / TST ID / Example Shell	Title	Programming Notes	Deliverable [Priority]
3.10.	Safety	AE15	Summary of Common (>=5%) Non-serious Adverse Events by System Organ Class and Preferred Term (Number of Subjects and Occurrences) - Part B		SAC
3.11.	Safety	AE16	Summary of Serious Adverse Events by System Organ Class and Preferred Term (Number of Subjects and Occurrences) – Part A		SAC
3.12.	Safety	AE16	Summary of Serious Adverse Events by System Organ Class and Preferred Term (Number of Subjects and Occurrences) – Part B		SAC
Laboratory Measurements					
3.13.	Safety	LB1	Summary of Clinical Chemistry Values – Part A		SAC
3.14.	Safety	LB1	Summary of Clinical Chemistry Values – Part B		SAC
3.15.	Safety	LB1	Summary of Change from Baseline for Clinical Chemistry Values – Part A		SAC
3.16.	Safety	LB1	Summary of Change from Baseline for Clinical Chemistry Values – Part B		SAC
3.17.	Safety	LB1	Summary of Haematology Values – Part A		SAC
3.18.	Safety	LB1	Summary of Haematology Values – Part B		SAC

Safety Tables					
No.	Population	IDSL / TST ID / Example Shell	Title	Programming Notes	Deliverable [Priority]
3.19.	Safety	LB1	Summary of Change from Baseline for Haematology Values – Part A		SAC
3.20.	Safety	LB1	Summary of Change from Baseline for Haematology Values – Part B		SAC
3.21.	Safety	UR3	Summary of Urinalysis Dipstick Results – Part A		SAC
3.22.	Safety	UR3	Summary of Urinalysis Dipstick Results – Part B		SAC
ECG					
3.23.	Safety	EG1	Summary of ECG Findings – Part A		SAC
3.24.	Safety	EG1	Summary of ECG Findings – Part B		SAC
3.25.	Safety	EG2	Summary of ECG Values – Part A		SAC
3.26.	Safety	EG2	Summary of ECG Values – Part B		SAC
3.27.	Safety	EG2	Summary of Change from Baseline for ECG Values – Part A		SAC
3.28.	Safety	EG2	Summary of Change from Baseline for ECG Values – Part B		SAC
Vital Signs					
3.29.	Safety	VS1	Summary of Vital Signs – Part A		SAC

Safety Tables					
No.	Population	IDSL / TST ID / Example Shell	Title	Programming Notes	Deliverable [Priority]
3.30.	Safety	VS1	Summary of Vital Signs – Part B		SAC
3.31.	Safety	VS1	Summary of Change from Baseline for Vital Signs – Part A		SAC
3.32.	Safety	VS1	Summary of Change from Baseline for Vital Signs – Part B		SAC

